#### Subgroup analyses

During the analysis of blinded data, possible convergence issues of the conditional logistic regression have been discovered for individual imputation datasets, but not all imputation

Trial ID: LP0162-1346	Date: 21-OCT-2020	Version: v1.0 Page 14 of 35
-----------------------	--------------------------	--------------------------------

datasets at once. This might not happen when the trial is unblinded, but in the event that it does, the analysis methods for the test of interaction can be re-opened for individual subgroup analyses if this issue is discovered. If this were to occur on unblinded data, the first step will be to relax the convergence criterion from the standard of  $1 * 10^{-8}$  to  $1 * 10^{-6}$ . If other measures are needed, it will be documented in the clinical trial report.

### **6.6.3.2 Continuous secondary endpoints**

#### Primary analysis of primary continuous estimand ('hypothetical')

Some subjects may not have any post-baseline data collected before initiation of rescue medication, have permanently discontinued IMP, or having subject-onset of the COVID-19 pandemic prior to the first post-baseline assessment. To ensure that all eligible subjects are included in the analysis, the baseline value will be carried forward as the first post-baseline assessment for these subjects, corresponding to imputing a change of 0 at the first post-baseline assessment. Additionally, subjects might be early terminated from the trial prior to the first scheduled post-baseline assessment with an assessment being done at the early termination visit. In this case the last assessment (including the baseline assessment) done prior to the first scheduled post-baseline assessment will be carried forward to the first scheduled post-baseline assessment.

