	
 • A helminth parasitic infection within 6 months prior to the date informed consent is obtained. • Tuberculosis requiring treatment within the 12 months prior to screening. • Known primary immunodeficiency disorder.
Investigational medicinal products	
Tralokinumab
 
 • Tralokinumab is a human recombinant monoclonal antibody of the immunoglobulin G4 (IgG4) subclass that specifically binds to human interleukin (IL) 13 and blocks interaction with the IL-13 receptors. • Active substance: tralokinumab. • Dosage form: solution (in accessorised pre-filled syringe, 1.0 mL fill volume). • Concentration: 150 mg/mL. • Dose: 300 mg every 2 weeks (Q2W) following an initial loading dose of 600 mg • Method of administration: Subcutaneous (SC). 
Placebo
 
 • Placebo contains the same excipients in the same concentration only lacking tralokinumab.
Auxiliary medicinal product (AxMP)	
TCS (Europe: Class 3 [potent])
 
Mometasone furoate, 0.1% cream provided in kit sizes of 180–225 g every 2 weeks.

Duration of treatment	
Each subject's trial participation will be up to 46 weeks, divided into a screening period (including washout, if applicable) of up to 6 weeks, a treatment period of 26 weeks, and a follow-up period of 14 weeks.
 
Eligible subjects may be invited to enter a long-term extension trial conducted under a separate protocol (LP0162-1337, ECZTEND). Subjects who transfer to ECZTEND must have had their last visit in the treatment period (Week 26 under the current protocol).

Number of subjects	A total of 250 subjects will be randomised 1:1 to treatment with tralokinumab 300 mg+TCS or placebo+TCS.
Number and distribution of trial sites	Up to 40 clinical sites in Europe are anticipated. Distribution between countries will be based on feasibility. Inclusion of subjects from Germany is prioritised.

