14.1 Sample size

With a significance level of 5%, a sample size of 250 subjects will provide 99% power for detecting a treatment difference for the primary endpoint, assuming an EASI75 response rate at Week 16 of 40% vs 15% for tralokinumab+TCS and placebo+TCS, respectively. Assuming a response rate of 30% vs 15% in reduction of Worst Daily Pruritus NRS (weekly average) score of at least 4 from baseline to Week 16 for tralokinumab+TCS and placebo+TCS, respectively, the trial will provide at least 80% power for rejecting the hypotheses related to the primary endpoint and the secondary endpoint evaluating pruritus at Week 16.

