14.3.9.1 Primary estimand for the continuous secondary endpoints: ‘hypothetical’

The primary estimand for the continuous secondary endpoints will be:

- Treatment difference in change from baseline to Week 16/ Week 26 in SCORAD and DLQI scores, respectively, if all subjects adhered to the treatment regimen in the sense that they did not discontinue IMP permanently, no rescue treatment was made available, and as if the COVID-19 pandemic did not happen before Week 16/ Week 26.

The primary estimand assesses the expected benefit when adhering to the treatment regimen tralokinumab+TCS with no rescue treatment or subject-onset of the COVID-19 pandemic as compared to a treatment regimen with placebo+TCS with no rescue treatment or subject-onset of the COVID-19 pandemic.

Primary analysis of the primary estimand (continuous secondary endpoints)

Data collected after permanent discontinuation of IMP, after initiation of rescue treatment, or after subject-onset of the COVID-19 pandemic will not be included in the analysis (Panel 13).

The endpoints will be analysed using a repeated measurements model on the post-baseline responses up to Week 26 with an unstructured covariance matrix, Kenward-Roger approximation to estimate denominator degrees of freedom, and the mean modelled as follows (shown for change from baseline in SCORAD):

Change from baseline in SCORAD

$$= \text{treatment} \times \text{visit} + \text{baseline SCORAD} \times \text{visit} + \text{prior CSA use} + \text{country} + \text{baseline IGA}$$

This model assumes that data is MAR within each treatment group. The estimates will be presented with nominal p-values and 95% CI at each visit. The comparisons between tralokinumab+TCS and placebo+TCS will be at Week 16 and Week 26.

Sensitivity analysis for the primary estimand (continuous secondary endpoints)

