14.3.10 Analysis of other endpoints

All binary endpoints listed under ‘Other endpoints’ (Panel 4) will be analysed as for the primary analysis of the primary and secondary estimands for the primary endpoint and presented for the FAS at Week 16 and Week 26.

All continuous endpoints listed under ‘Other endpoints’ (Panel 4) will be analysed as for the primary analysis of the primary and secondary estimands for the continuous secondary endpoints. For the Eczema-related Sleep NRS score, the mean over the last 7 days prior to randomisation will be used as the baseline value. For the Worst Daily Pruritus NRS and Eczema-related Sleep NRS scores, it is expected that subjects will return their eDiaries upon permanent discontinuation of IMP, and no data is available after that point. Thus, analysis

using the primary analysis of the secondary continuous estimand will not be possible in the ‘Other endpoints’ with Worst Daily Pruritus NRS or Eczema-related Sleep NRS scores.

To evaluate the efficacy related to health care resource utilisation, the amount of TCS used (assessed as the amount of TCS used between visits) will be determined over 2-week periods, and the number of days without topical treatment use (collected as Patient Days of Topical Treatment Use in the eDiary) will be determined over 1-week periods. The amount of TCS used and the number of days without topical treatment use will each be analysed using a repeated measurements model with an unstructured covariance matrix and the mean modelled as follows:

$$Y = \text{treatment} \times [\text{visit/week}] + \text{prior CSA use} + \text{country} + \text{baseline IGA}$$

where ‘Y’ is either the amount of TCS used or the number of days without topical treatment use. Data obtained after permanent discontinuation of IMP, after initiation of rescue treatment, or after subject-onset of the COVID-19 pandemic will be excluded from the analyses.

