14.3.16 General principles

Unless otherwise stated, all significance tests will be 2-sided using the 5% significance level. All CIs will be presented with 95% degree of confidence. An observed-cases approach will be used for tabulations of data by visit (i.e. involving only those subjects who attended each specific visit).

Categorical data will be summarised using the number and percentage of subjects in each category and treatment group. Continuous data will be summarised using the mean, median, standard deviation, 1st quartile, 3rd quartile, minimum, and maximum values.

All the analyses specified in the protocol will be reviewed in relation to the blinded data actually obtained and the statistical analysis plan and the analysis set definition document will be finalised before breaking the randomisation code.

Any changes from the statistical analysis planned in this clinical trial protocol will be described and justified in a protocol amendment, the statistical analysis plan, and/or in the CTR dependent on the type of deviation.

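### The SCORAD and DLQI repeated-measures model takes in a fixed zero change as observed data, against the hypothetical estimand and its MAR assumption; the effect is probably small and its direction unknown

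*SAP*

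**What the plan says.** Protocol Section 14.3.9.1 defines the primary estimand for the changes in SCORAD and DLQI as hypothetical: the difference had nobody stopped IMP permanently, had rescue not been available, and had the pandemic not happened. Data after any of these events are left out. The analysis is a repeated-measures model with unstructured covariance, and the protocol adds: "This model assumes that data is MAR within each treatment group". Panel 13 lists post-event and missing values as not used in this analysis and shows no single imputation. Under Section 14.3.6, hypothesis tests rest on the primary analysis of the primary estimand, so this model carries the confirmatory tests for both scores.

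SAP Section 6.6.3.2 then deals with subjects who have no post-baseline data before their first intercurrent event. For them, "the baseline value will be carried forward as the first post-baseline assessment for these subjects, corresponding to imputing a change of 0". The only reason given is that all eligible subjects should be in the analysis. Footnote 2 of Table 9 and Section 6.8.5 implement the rule as an LOCF record. The SAP change log in Section 4 does not list it.

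The continuous endpoints in the protocol's Other group "will be analysed as for the primary analysis of the primary and secondary estimands for the continuous secondary endpoints" (Protocol Section 14.3.10), so the rule appears to reach them too.

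**The concern.** A change of 0 says that the subject did not improve at all by the first visit. It is not a prediction from the MAR model, and nothing in the documents makes it the outcome expected under adherence without rescue. The model also takes it as known, with no added uncertainty.

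The rest of the plan treats such subjects differently:

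- For the hypothetical estimand of EASI75 (Protocol Section 14.3.8.4), a missing Week 2 EASI is imputed by regression under MAR. The same subject is set to no change for SCORAD.
- In the COVID-19 modified composite estimand for the continuous endpoints (Protocol Section 14.3.9.3), rescue or discontinuation leads to the worst observation, baseline included. With no other observation this is also a change of 0. The SAP rule therefore brings a composite-type value into the hypothetical analysis.
- In that same composite estimand, subjects with pandemic onset are imputed under MAR. In the hypothetical analysis they receive the zero.

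At stake is whether the confirmatory SCORAD and DLQI estimates target the estimand they are reported under.

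**Working it through.** **1. The plan's own figure.** The plan gives no number that depends on this rule. Its power statement confirms the sample size used below. "A total of 250 subjects will be randomised 1:1 to treatment with tralokinumab 300 mg+TCS or placebo+TCS" gives 125 per arm. Section 14.1 assumes EASI75 rates of 40% and 15%, and the test is two-sided at 5%.

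- Pooled rate 0.275: null SE = √(2 × 0.275 × 0.725 / 125) = 0.0565.
- Alternative SE = √((0.40 × 0.60 + 0.15 × 0.85) / 125) = 0.0542.
- z = (0.25 − 1.96 × 0.0565) / 0.0542 = 2.57, so power is 99.5% (stated: 99%).
- The same formula at 30% vs 15% gives 81.4%. Joint power is then at least 0.995 + 0.814 − 1 = 80.9%, in line with the stated minimum of 80%.

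These figures do not change with the point below.

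**2. How the zero reaches Week 16.** With an unstructured covariance and monotone dropout, the likelihood estimate of an arm's Week 16 mean uses its Week 2 mean, weighted by the Week 16-on-Week 2 slope. If a share f of the arm is given 0 in place of a mean improvement c, the Week 2 mean loses f × c of improvement and the Week 16 mean loses slope × f × c. Hence:

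shift in favour of tralokinumab = slope × (f_P × c_P − f_T × c_T)

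**3. Illustrative inputs (all assumed; the documents give none).** Mean Week 2 SCORAD improvement of 18 (tralokinumab) and 15 (placebo), slope 0.5, affected shares of 1–2% (tralokinumab) and 2–5% (placebo).

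| f_T | f_P | Calculation | Shift in favour of tralokinumab |
|---|---|---|---|
| 2% | 2% | 0.5 × (0.30 − 0.36) | −0.03 |
| 1% | 2% | 0.5 × (0.30 − 0.18) | +0.06 |
| 2% | 5% | 0.5 × (0.75 − 0.36) | +0.195 |
| 1% | 5% | 0.5 × (0.75 − 0.18) | +0.285 |

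**4. Wider inputs (assumed).** Week 2 improvement of 10–20 on tralokinumab and 10 on placebo, slope 0.4–0.8, shares 0–5% per arm. The extremes are 0.8 × 0.05 × 10 = 0.40 points in favour of tralokinumab (placebo only affected) and 0.8 × 0.05 × 20 = 0.80 points against (tralokinumab only affected).

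**5. Simulation check (assumed inputs).** 125 per arm; visits at Weeks 2, 8 and 16; mean changes −15, −25, −32 (tralokinumab) and −10, −17, −22 (placebo); SDs 12, 15, 17; a baseline covariate; affected subjects chosen at random; 1,500 runs. The true Week 16 difference is −10, and negative favours tralokinumab.

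| Affected (tralokinumab, placebo) | Without zero | With zero | Shift |
|---|---|---|---|
| 2%, 2% | −9.92 | −9.85 | +0.07 |
| 5%, 5% | −9.90 | −9.72 | +0.17 |
| 0%, 5% | −9.91 | −10.26 | −0.36 |
| 5%, 0% | −9.90 | −9.37 | +0.53 |

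Shifts are taken from unrounded values. Each pair uses the same random draws, so the common offset of about 0.1 from −10 cancels. The correlation of 0.5 between Weeks 2 and 16 implies a slope of 0.5 × 17/12 = 0.71. The formula then gives 0.71 × 0.05 × 10 = 0.35 and 0.71 × 0.05 × 15 = 0.53 for the last two rows, as simulated. The sampling SD of the difference was about 2.2 points throughout.

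**The case against.** The other side has several good arguments.

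- **The affected group is probably small.** SCORAD and DLQI are first assessed at Week 2. An event counts only if it precedes the visit date (SAP Section 6.8.6), and rescue begun on the day of an assessment is taken not to influence it (Protocol Section 14.3.5). A prolonged pandemic interruption cannot start before Week 6. This stands, and it limits the size of the effect.
- **A planned analysis of this estimand already appears to avoid the zero.** The copy-reference sensitivity analysis in Protocol Section 14.3.9.1 imputes missing Week 2 values by regression, and the SAP does not extend the carry-forward to it. A reader might infer that every planned analysis contains the zero; that would be wrong. But copy-reference departs from MAR by design, so a MAR analysis without the zero is still missing.
- **The rule has a purpose.** Analyses are to be based on the FAS, and with change from baseline as the response a subject without a post-baseline row leaves the model. This is a real cost, but the wish to include a subject does not make 0 a MAR value.
- **The outcome without rescue is unknown.** A reader might argue that these subjects would certainly have improved on TCS. The documents cannot show that for someone rescued or withdrawn before Week 2. The point does not need it: the conflict is with the model's stated assumption.

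A reader might also infer a larger bias for SF-36, EQ-5D-5L and HADS, first assessed after baseline at Week 8. More subjects could be affected there, but the documents give no changes, slopes or event rates from which to size it, and these endpoints lie outside the testing hierarchy.

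**Conclusion.** The point holds as a conflict between the SAP rule and the estimand, the MAR statement and Panel 13. It is a minor one on the likely numbers. Under the first set of assumptions the Week 16 SCORAD shift runs from 0.03 points against to 0.29 points in favour of tralokinumab, at most about 0.13 of the simulated sampling SD (0.285 / 2.2). No size was worked out for DLQI or for Week 26; the mechanism is the same.

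It is tempting to conclude that the rule favours tralokinumab. The documents do not support that, because they give no early-event rates by arm. More early events on placebo would favour tralokinumab. Equal shares would work slightly against it if tralokinumab improves more by Week 2. For the same reason the rule cannot be defended as conservative.

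The point concerns the inserted zero only. The second rule in SAP Section 6.6.3.2, for early termination before the first scheduled assessment, can carry forward a real post-baseline value.

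**What to change.** - Remove the carried-forward baseline row from the primary repeated-measures analysis, so that the likelihood handles these subjects under MAR.
- Keep the carry-forward version as a sensitivity analysis, labelled as a departure from MAR.
- Report the number of affected subjects per arm.
- Align SAP Section 6.6.3.2, Section 6.8.5 and footnote 2 of Table 9. The footnote limits LOCF to subjects with no scheduled post-baseline assessment at all, while Section 6.8.5 can be read to include those who only missed the first visit.
- If any form of the rule stays, enter it in the SAP change log as an addition to the protocol.

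The cost is SAP wording and one further model run. The downside is that FAS subjects with no usable post-baseline value contribute no post-baseline information. Putting baseline into the response vector (a constrained longitudinal model) would keep them in the model, but it replaces the protocol's mean model and is therefore optional.

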#### Primary analysis of the secondary continuous estimand ('treatment policy')

Due to the high chance of discontinued subjects opting not to attend the nominal Week 16 / 26 visits, a general conservative rule is put in place. In case within one of the 4 groups defined is 2 or less observed values the missing data will be imputed using the worst observation carried forward.

In the multiple imputation methods specified, the variables used in the imputation procedures will not be prior CSA use and baseline IGA, but prior CSA use, county (Germany Yes/No), and baseline IGA.

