14.3.9.2 Secondary estimand for the continuous secondary endpoints: 'treatment policy'

The secondary estimand for the continuous secondary endpoints will be:

- Treatment difference in change from baseline to Week 16/ Week 26 in SCORAD and DLQI scores, respectively, between tralokinumab+TCS and placebo+TCS regardless of rescue treatment use and treatment discontinuation, as if the COVID-19 pandemic did not happen.

The secondary estimand assesses the average difference in change from baseline in SCORAD and DLQI at Week 16/ Week 26, resulting from initiation of a treatment regimen with tralokinumab+TCS and rescue treatment as compared to a treatment regimen with placebo+TCS and rescue treatment.

Primary analyses for the secondary estimand (continuous secondary endpoints)

Data retrieved at Week 16/ Week 26 for subjects who prior to Week 16/Week 26 have permanently discontinued IMP for other reasons than the COVID-19 pandemic will be included in the analysis.

For subjects who have subject-onset of the COVID-19 pandemic prior to Week 16/ Week 26 and prior to any permanent discontinuation of IMP not due to the COVID-19 pandemic, any observed data from these subjects will be ignored and treated as missing in the same manner as missing data from not discontinued subjects in the analysis ([Panel 13](#)).

Missing Week 16/ Week 26 data will be imputed using multiple imputations assuming that data is MAR within the groups used for imputation.

Imputation of missing data at Week 16/ Week 26 will be done using multiple imputations within 4 groups defined according to randomised treatment group and whether or not subjects have discontinued treatment prior to Week 16/ Week 26. Within a given treatment group, retrieved data from discontinued subjects will be used to impute missing data for other discontinued subjects. Similarly, the available data from not discontinued subjects will be used to impute data for such subjects where the Week 16/ Week 26 value is missing/treated as missing.

For not discontinued subjects, the stepwise multiple imputations procedure will be conducted in the same way, using the same seeds, as specified for the imputation of the underlying EASI values in the primary analysis of the quaternary estimand for the binary endpoints (see [Section 14.3.8.4](#)).

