#### Primary analysis of the tertiary estimand ('treatment policy')

As stated in the protocol, it is expected that the number of observed values in the 2 treatment groups of discontinued subjects is too small to facilitate MI of data using Rubin's rule. In this case, the primary analysis will be substituted with the sensitivity analysis. A limit of 2 or less observed values within each of the treatment groups of discontinued subjects will be used to enforce when the sensitivity analysis will become the primary analysis.

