#### Sensitivity analysis of the secondary continuous estimand ('treatment policy')

As for the primary analysis of this estimand, the sensitivity analysis will also have the general rule applied if there are not enough observed data to facilitate MI of data. Since the MI in this sensitivity analysis applies a copy-reference approach, only the discontinued/non-discontinued subjects randomised to placebo are applicable for this. The rule will, again, be that if there are 2 or less observed values at the analysed visit in the respective placebo group

Trial ID: LP0162-1346	Date: 21-OCT-2020	Version: v1.0 Page 15 of 35
-----------------------	-------------------	--------------------------------

then missing data within the group will be imputed using the worst observation carried forward.

In the multiple imputation methods specified, the variables used in the imputation procedures will not be prior CSA use and baseline IGA, but prior CSA use, county (Germany Yes/No), and baseline IGA.

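### The sparse-data fallback for SCORAD and DLQI (treatment policy) can put one arm alone on worst observation carried forward; if that arm is placebo, the shift favours tralokinumab

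*SAP*

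**What the plan says.** **SCORAD and DLQI, primary analysis.** Protocol 14.3.9.2 imputes Week 16 and Week 26 data by "multiple imputations within 4 groups defined according to randomised treatment group and whether or not subjects have discontinued treatment". Each arm's discontinued subjects are therefore a group of their own. SAP 6.6.3.2 expects many discontinued subjects to skip the nominal visits, and adds a fallback: "In case within one of the 4 groups defined is 2 or less observed values the missing data will be imputed using" WOCF. The SAP presents this fallback by saying that "a general conservative rule is put in place". It does not say what happens to the matching group in the other arm.

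**SCORAD and DLQI, sensitivity analysis.** This is a copy-reference analysis, with both arms imputed from placebo. The SAP notes that "only the discontinued/non-discontinued subjects randomised to placebo are applicable for this". If the respective placebo group has 2 or fewer values, "then missing data within the group will be imputed using the worst observation carried forward".

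**EASI75, same type of estimand.** SAP 6.6.2 sets the trigger differently: "A limit of 2 or less observed values within each of the treatment groups of discontinued subjects will be used". The consequence also differs: "the primary analysis will be substituted with the sensitivity analysis". That changes the handling in both arms together, in line with protocol 14.3.8.3.

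**WOCF.** SAP 6.8.7 takes the worst value from baseline up to the analysed visit, baseline included. The imputed change is therefore zero or a worsening.

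**The concern.** The SCORAD/DLQI trigger is checked group by group, and the natural reading is that only the group that falls short changes method. The two arms can then be imputed by different rules in one comparison, depending on how many discontinued subjects in each arm happened to attend a nominal visit.

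The direction depends on which arm falls short. If it is tralokinumab, the difference shrinks and the rule is conservative. If it is placebo, placebo's missing discontinued subjects are given no improvement or worse, while tralokinumab's are still imputed from a model fitted to that arm's own retrieved values. As long as retrieved drop-outs improved on average, this widens the difference in favour of tralokinumab. The SAP nevertheless calls the rule conservative without condition.

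At stake are the treatment-policy results for SCORAD and DLQI at Weeks 16 and 26. By reference, the SCORAD/DLQI subgroup analyses (protocol 14.3.9.4) and the continuous other endpoints apart from the eDiary scores (14.3.10) are affected too. The count is taken per endpoint and visit, so the handling could differ between analyses shown side by side.

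**Working it through.** **The plan's own figures.** The plan gives no figure for this rule. The only number borrowed from it is about 125 per arm (250 randomised 1:1). Its power statement reproduces: 125 per arm, 40% vs 15%, two-sided 5% gives 99.5% against the stated 99%.

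**Assumptions not in the documents.** Retrieved counts, missing counts, the improvement of retrieved drop-outs, and an SD of 18 for SCORAD change are all assumed. The ranges are shown below.

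**Step 1: chance that placebo alone triggers.** Let the retrieved values in each arm's discontinued group be independent Poisson counts with a common mean, and let p be the probability of 2 or fewer. Then P(exactly one arm) = 2p(1−p), and P(placebo only) = p(1−p).

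| Mean | p | Exactly one arm | Placebo only |
|---|---|---|---|
| 0.5 | 0.986 | 3% | 1% |
| 1 | 0.920 | 15% | 7% |
| 2 | 0.677 | 44% | 22% |
| 3 | 0.423 | 49% | 24% |
| 4 | 0.238 | 36% | 18% |
| 5 | 0.125 | 22% | 11% |

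Below a mean of about 2, both arms mostly trigger together and are treated alike.

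A binomial check uses retrieval rates of 20–50%. With 5, 8 or 10 discontinued in each arm, placebo-only triggering is 5–25%. With 8 discontinued on tralokinumab and 12 on placebo, it is 2–11%, and tralokinumab-only is 14–41%.

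**Step 2: shift when one arm triggers.** Let m be the missing discontinued subjects in that arm, and D the gap between the mean WOCF change and the mean change that imputation from retrieved values would give. The shift in the treatment difference is (m/125) × D. Taking the WOCF change as 0, D is the improvement of retrieved drop-outs.

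- Low: 4/125 × 10 = 0.32 SCORAD points.
- High: 12/125 × 20 = 1.92 SCORAD points.
- SE of the difference: 18 × √(2/125) = 2.28. This is a plain two-sample SE that ignores covariates and imputation variance.
- In SE units: 0.32/2.28 = 0.14 and 1.92/2.28 = 0.84.

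Wider inputs (m = 3–13) give 3/125 × 10 = 0.24 to 13/125 × 30 = 3.12 SCORAD points, and for DLQI 3/125 × 3 = 0.07 to 13/125 × 9 = 0.94 points.

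**Step 3: effect of a symmetric rule.** If both arms switch and D is equal in the arms, the tralokinumab-minus-placebo shift is (m_T − m_P)/125 × D. A negative value favours tralokinumab. With D = 20:

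| Missing T, P | Placebo only | Tralokinumab only | Both arms |
|---|---|---|---|
| 6, 6 | −0.96 | +0.96 | 0.00 |
| 6, 10 | −1.60 | +0.96 | −0.64 |

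**The case against.** **Scope is inferred.** SAP 6.6.3.2 does not state that WOCF is confined to the group that triggers it. The sensitivity analysis speaks of missing data within the group, but that analysis imputes both arms from placebo, so there the group may have to mean discontinuation status across arms. This objection stands in part. The one-arm reading of the primary analysis is the natural one, because the four groups are arm-specific, but it is not explicit. On the alternative reading the text still needs to say so. On the one-arm reading of the sensitivity analysis, tralokinumab's missing discontinued subjects have no stated rule when placebo falls short.

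**The EASI75 contrast.** A reader might infer that EASI75 switches only when both arms fall short. The documents do not settle this: 'within each' can mean either arm or both. What is clear is that the EASI75 switch, once made, covers both arms.

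**Type I error.** A reader might infer that the trial's false-positive rate is inflated. It is not. Protocol 14.3.6 bases testing on the primary estimand, which for SCORAD and DLQI is the hypothetical one, analysed without this rule. The high-end shift would raise a nominal one-sided 2.5% rate to 1 − Φ(1.96 − 0.84) = 13.2%, and the low end to 3.4%, but only given that placebo alone triggers. Averaged over all trigger outcomes at a mean of 3, the same inputs give about 2.6–4.6%.

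**A symmetric analysis exists.** The tertiary continuous estimand (protocol 14.3.9.3) applies WOCF in both arms. It is useful context but a different question, since it also applies WOCF after rescue and over observed values. The copy-reference analysis is no independent check, because it has its own WOCF fallback, triggered by placebo counts.

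**Conclusion.** The concern holds as a limited one. On its natural reading, the SCORAD/DLQI fallback allows different imputation rules in the two arms, and its conservative label is wrong when placebo alone triggers it. The direction follows from the WOCF definition, provided retrieved drop-outs improve on average.

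The size is small to moderate and rests wholly on assumptions: 0.32–1.92 SCORAD points (0.14–0.84 SE) when one arm triggers. The chance that placebo alone triggers is about 11–24% for an equal mean of 2–5 retrieved values per arm. It is lower if very few values are retrieved, when both arms tend to switch together, or if placebo has more discontinuers, when tralokinumab-only triggering is the likelier one-arm case. Confirmatory conclusions are not touched. The rule should be made symmetric because the present wording lets attendance decide the direction of the bias.

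**What to change.** - **SAP 6.6.3.2, primary analysis of the secondary continuous estimand.** State: *If either arm's discontinued group has 2 or fewer observed values at the visit, missing data of discontinued subjects in both arms are imputed by WOCF; likewise for the not-discontinued groups.* Do not describe a one-arm rule as conservative.
- **SAP 6.6.3.2, sensitivity analysis.** Keep the trigger on the respective placebo group, since the copy-reference model is fitted only there. Apply WOCF to the missing data of the corresponding group in both arms. Extending the trigger itself to tralokinumab would discard a model that can be fitted.
- **SAP 6.6.2, tertiary estimand for EASI75.** Replace 'within each' with 'within either', so that a shortfall in one arm also switches the whole analysis.

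The cost is SAP wording and a few lines of code. One arm's retrieved data will sometimes go unused for imputation although its model could be fitted. Some shift also remains when the arms differ in missing counts (0.64 instead of 1.60 points in the 6 vs 10 example) or in how far retrieved drop-outs improved.
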